15.4 Guidelines for the Premature Termination of the Trial

Guidelines for the premature termination of the trial are summarised below. However, advice and recommendations from the TSC based on information from the IDMC and with input from the NIHR may consider premature termination of the trial for other reasons besides those considered below.

- If both experimental treatment arms are futile at the interim analysis.
- Safety reasons. The IDMC will review blinded data periodically.
- Following guidance from the IDMC, TSC and also NIHR, if it is unfeasible to continue the trial.

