15.2 Interim Analyses

Interim analyses are scheduled for approximately 18 months after the first participant is enrolled but may be later in the trial depending on recruitment and number of events (i.e. exacerbations). The choice is flexible and only has a minor impact on the expected number of events over a range of hazard ratios. The total number of observed events across 3 arms is expected to be around 350 at 18 months, with around 700 recruited; the interim analyses may be rescheduled if the number of events or recruits is substantially out from these predictions. These analyses will inform a recommendation to drop a treatment arm on the basis of futility made by the trial's DMC (the standard care arm will always be continued). This decision will be informed by Bayesian posterior distributions for the treatment effects on the primary outcome of each experimental treatment. Based on a vague prior distribution with 95% weight between hazard ratio of 0.5–2.0, an early stopping guideline would be if a posterior distribution gave more than 70% probability to a hazard ratio higher than 1.25.

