The trial design has been set up for a long period of follow-up relative to assumed time to primary events, to enable evaluation of the secondary endpoints of the trial. Although the trial is not powered for secondary endpoints, to accrue data regarding hospitalisations and mortality in this cohort, not only on the trial IMP but also back on their regular azithromycin prescription, is considered *a priori* an important aim of the trial. There is a lack of data on hospitalisation and mortality rates in this population (people with COPD on long term azithromycin). Given that there has been no trial evaluating complete or seasonal discontinuation of antibiotic prophylaxis in COPD, it is desirable to ensure that the trial does not stop before sufficient information is gathered to provide a definitive result. However, it is recognised that there may be reasons for stopping the trial earlier than anticipated, for example due to overwhelming evidence of efficacy or safety, or if the target number of events have occurred and it is considered not appropriate to continue the trial for secondary endpoints accrual. Data from the IDMC and advice and recommendations from the TSC will determine this.

For these reasons, one formal interim analysis is planned as described in section 15.2.

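### Section 15.4 rests the IDMC's periodic safety review on blinded data, which, if pooled, cannot show harm confined to one withdrawal arm; a lesser point is that 15.3.1 mentions efficacy stopping without a boundary

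*Protocol*

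**What the plan says.** **Safety review.** Section 15.4 lists grounds for premature termination. The safety entry reads "Safety reasons. The IDMC will review blinded data periodically". The same section leaves the list open: the TSC, informed by the IDMC and with NIHR input, "may consider premature termination of the trial for other reasons besides those considered below". Section 15.3.1 uses the word blinded for event-rate monitoring, where it means without knowledge of the allocated arm. It also says: "There is a lack of data on hospitalisation and mortality rates in this population". Under section 11.1.4.1, COPD exacerbations, pneumonia and the admissions they cause are recorded as outcomes and are not considered or reported as AEs or SAEs.

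**By-arm look.** Section 15.2 gives the DMC an analysis at about 18 months or later: "These analyses will inform a recommendation to drop a treatment arm on the basis of futility". It continues: "This decision will be informed by Bayesian posterior distributions for the treatment effects on the primary outcome of each experimental treatment". The guideline is explicit: "an early stopping guideline would be if a posterior distribution gave more than 70% probability to a hazard ratio higher than 1.25".

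**Efficacy.** Section 15.3.1 recognises that the trial might stop early, "for example due to overwhelming evidence of efficacy or safety", and then says that for these reasons "one formal interim analysis is planned as described in section 15.2". Section 15.1 sets one-sided 97.3% intervals for the two final comparisons so as to keep an overall 5% level.

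**The concern.** Two of the three arms withdraw azithromycin, one fully and one for half of each year. Any harm from withdrawal is a difference between arms, and a committee that sees only pooled figures cannot see that difference. The usual fallback is to compare the pooled rate with an expected rate, and the protocol itself says such data are lacking. The most plausible severe harm, admission for exacerbation or pneumonia, also bypasses SAE reporting. Read literally, the safety sentence would allow an arm-specific excess of deaths or admissions to go unrecognised between the start of the trial and the interim. The interim itself is described only for the primary outcome.

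The sentence also fits poorly with section 15.2, where the same committee has to work from results for each experimental arm.

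The second, smaller concern is error control. If efficacy can stop the trial, the level at which it does so matters, and the whole 5% is already assigned to the final comparisons.

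**Working it through.** **1. What pooled data would show.** Allocation is 1:1:1 (sections 7.1 and 8.3). With equal follow-up per arm and a rate ratio *h* in one arm only, the pooled rate ratio is (1 + 1 + h)/3.

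| True ratio in one arm | Pooled ratio |
|---|---|
| 1.25 | 3.25/3 = 1.08 |
| 1.5 | 3.5/3 = 1.17 |
| 2.0 | 4/3 = 1.33 |

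If both withdrawal arms doubled, the pooled ratio would be (1 + 2 + 2)/3 = 1.67. In no case could the excess be attributed to an arm, and the protocol gives no baseline rate against which to read it.

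**2. The passages side by side.** Section 15.2 has the DMC consider a posterior distribution for each experimental treatment against control, which needs data by arm. Section 15.4 has the IDMC review blinded data for safety. No by-arm review of deaths, admissions, AESIs or SAEs is stated in either section.

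**3. The plan's event count.** Inputs are margin HR 1.25, one-sided 2.7% per comparison and 90% power (sections 15.1 and 15.3). Schoenfeld's formula for one pair of equal arms gives

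d = 4(z₀.₉₇₃ + z₀.₉₀)²/(ln 1.25)² = 4(1.927 + 1.282)²/(0.2231)² ≈ 827.

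That is 414 per arm, and 3 × 414 = 1242, the stated number. The plan is therefore sized for a single final analysis with nothing set aside for an earlier efficacy look. With correlation 0.5 between the two comparisons, one-sided 2.7% on each gives a family-wise error of 4.89%, about 0.1 point below 5%.

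**4. Adding one efficacy look.** About 350 events are expected at the interim (section 15.2), so the information fraction is 350/1242 = 0.282 and the correlation between looks is √0.282 = 0.53. The final level stays at one-sided 2.7%. The interim thresholds are assumptions, because the protocol gives none. Futility stopping is ignored.

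| Interim one-sided level | Error per comparison | Family-wise error |
|---|---|---|
| no look | 2.70% | 4.89% |
| 0.0005 | 2.73% | 4.93% |
| 0.001 | 2.76% | 4.99% |
| 0.005 | 3.04% | 5.49% |
| 0.01 | 3.42% | 6.17% |
| 0.027 (unadjusted) | 4.84% | 8.59% |

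One pair has about 350 × 2/3 = 233 events at the interim, so the standard error of the log hazard ratio is 2/√233 = 0.131. A claim at p<0.001 would then need an estimated hazard ratio below about 0.83; at the unadjusted level, below about 0.97.

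**5. Holding 2.7% per comparison exactly.** O'Brien-Fleming-type spending uses 0.00003 at the interim and leaves 0.02699 for the final test, with power 90.0% at 1242 events. A fixed 0.001 look leaves 0.0264, with power 89.9%.

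**The case against.** **The word blinded is not defined in 15.4.** The definition in 15.3.1 belongs to event-rate monitoring for sample size. Reports by coded arm (A/B/C) could also be called blinded and would allow a comparison. Section 17 leaves the IDMC's remit to a charter, and 15.1 promises an interim SAP; neither is shown. This stands as a reason for caution about what will happen in practice. It does not rescue the sentence. The only explanation of the term in the protocol points to pooled data, and a charter providing open by-arm review would contradict 15.4 as written.

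**A reader might infer that the early-stopping rules as a whole do not work, or that the IDMC must stop the trial on blinded data.** The documents do not support either. The futility guideline is by arm and can be applied. Section 15.4 does not say that a safety decision must be taken blind, and the IDMC informs advice from the TSC and NIHR; it does not stop the trial itself.

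**A reader might infer that the IDMC is the only safeguard.** It is not. Section 8.7 has an individual rule for stopping trial medication, section 8.6 allows withdrawal on medical grounds, section 8.5 provides emergency unblinding, and other SAEs are reported within 24 hours (section 11.5). None of these compares arms, so the gap remains, but it is narrower than that inference.

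**On efficacy**, 15.3.1 acknowledges a possibility and does not set a rule; 15.4 does not list it, and boundaries are often left to an interim SAP. This is fair and makes the point minor. What remains is a mismatch inside the protocol: 15.3.1 mentions efficacy and refers to an interim that has only a futility purpose.

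**Conclusion.** The safety point holds as a defect of wording with consequences for participants. If blinded in 15.4 means pooled, a doubled rate of death or admission in one withdrawal arm would appear as a 1.33-fold pooled rate, with no benchmark and no arm attached. This assumes equal arm sizes and follow-up. It rests on reading the term as 15.3.1 uses it; under arm-coded reporting the problem would largely go, but the protocol does not say so. Under either reading, 15.4 needs reconciling with the by-arm role in 15.2.

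The efficacy point holds as a minor inconsistency. It would be wrong to infer that stopping for efficacy necessarily breaks the 5% level. Family-wise error runs from 4.93% to 8.6% over the thresholds tried, and 8.6% is a conditional worst case that needs non-inferiority to be claimed at about 350 events at the unadjusted level. The protocol proposes no such test, and so loose a level is hard to square with evidence described as overwhelming. The sample size of 1242 events is not in question.

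**What to change.** **Section 15.4.** Replace the sentence on blinded review with a statement that, at each meeting, the IDMC reviews deaths, hospitalised exacerbations, pneumonia, AESIs and SAEs by arm in a closed report, with the trial team and TSC kept blind. Align the IDMC charter. The cost is a wording amendment and the preparation of unblinded closed reports more often than the single interim already requires.

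**Section 15.3.1.** Either delete efficacy as a reason to stop early, or name a strict bound there and in 15.2. One-sided p<0.001 at about 350 events keeps family-wise error at 4.99% with the final 97.3% level and 1242 events unchanged. If 2.7% per comparison is to be held exactly, an O'Brien-Fleming-type bound does so with no change in events. If a bound is named, the text should also say what efficacy means at the interim, since non-inferiority is the only formal conclusion defined in 15.1. The cost is wording only.

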15.5 Procedure to account for Missing or Spurious Data

The primary endpoint is a time-to-event endpoint. If a participant withdraws fully or completes full follow-up, before experiencing their first exacerbation then their observation is treated as a censoring.

Secondary and exploratory endpoints may be still observed even if a participant withdraws from protocolised treatment, and thus will be analysed. The proportion of missing values will be reported, and a default analysis will be based on complete cases, thus assuming Missing Completely At Random. Further sensitivity analyses will be detailed in a SAP.

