15 STATISTICS

15.1 Statistical Methods

A Statistical Analysis Plan (SAP) will be written and approved by the TSC and NIHR. A version of the SAP outlining the key aspects of the primary analysis, will be produced before any efficacy data is examined by the independent data monitoring committee (iDMC), TSC, or any members of the trial team. An interim SAP will be produced before any interim analysis is performed.

The primary endpoint is time to first exacerbation. The experimental treatments are complete discontinuation, seasonal discontinuation, and the control arm is continued azithromycin (this is standard of care). The hazard ratio comparing the two experimental arms to control will be estimated using a Cox proportional hazards model, adjusting for pre-randomisation factors of exacerbations history (number in preceding 12 months) and recruitment site. The consensus decision of the project team was that recruitment site and history of previous exacerbations (given this is the strongest predictor of exacerbations) are appropriate pre-specified covariates. Formal inference will compare the 1-sided confidence interval to the non-inferiority margin of a hazard ratio of 1.25. If the interval lies entirely below 1.25 then a conclusion of non-inferiority will be made. The confidence intervals will be at a 97.3% level, to adjust for there being two comparisons, and thus preserve an overall 5% significance level. The primary analysis will be an Intention to Treat analysis.

For the panel of subgroup factors to consider (section 15.1.1-15.1.2), the analysis will estimate the main effect and a treatment-subgroup interaction on the hazard ratio scale, adjusting for baseline covariates used in the primary analysis. This will be carried out in a univariate fashion, looking at each subgroup individually. Potentially, a multivariate model will be developed to include multiple subgroups simultaneously and provide a risk score. Standard 95% confidence intervals for the estimated subgroup-treatment interaction hazard ratio will be the primary focus. Multiple testing would preclude making strong claims of formal statistical significance; and any personalised treatment strategy would need to be validated in future research.

Secondary endpoints will be analysed using a similar regression methodology, as suitable for the nature of the endpoint (binary, categorical, continuous, time-to-event). The rate of

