exacerbations will be evaluated by dividing number of exacerbations by person-years of follow-up and will be analysed with both Poisson and negative-binomial analyses.

Missing data will be quantified for each endpoint broken down by treatment arm. The reference analyses will assume missing at random, conditional on the baseline covariates used for adjustment. Should the rate of missing data exceed 10%, then multiple imputation will be used in sensitivity analyses that consider alternative assumptions incorporating selection bias.

15.1.1 Pre-specified subgroup analysis

The aim of this subgroup analysis is to identify factors that may practically support front line clinicians in shared decision making for individual patients. Selection of subgroup variables have been considered in-depth based on post-hoc evidence of azithromycin prophylaxis trials in COPD, and consideration of generalisability to clinical practice. The limitations of subgroup analyses are recognised. We have tried to limit multiplicity and plan to undertake and report subgroup analysis as per recommended criteria.⁶³ Subgroup analysis will be performed for the trial's primary endpoint, as well as secondary outcomes of exacerbation rate (including severe exacerbations analysed separately) and side effects/risks, evaluated on IMP.

15.1.2 Top priority subgroup analysis:

- Exacerbation history (number in last 12 months): Strongest predictor of future exacerbations.³⁵
- **FEV1 %:** In two trials milder airflow obstruction was associated with greater treatment efficacy of azithromycin in COPD, although trial populations may not be reflective of real-world COPD patients prescribed azithromycin. (i.e. one trial-not frequent exacerbators, other included GOLD stage 1).^{4,31,43}
- **Smoking status:** Current smoking may affect azithromycin efficacy.³¹ Important to evaluate, NICE recommend only in non-smokers specifically, BTS recommend smoking cessation optimisation prior to starting treatment.^{1,2}
- **CAT score (symptom burden/impact):** NICE recommend evaluation of prognostic factors in COPD care because of potential therapy implications.¹ Of prognostic factors, CAT score is likely most useful to evaluate.

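### Sections 15.1 and 15.5 name different, unranked missing-data assumptions for the main analysis of the secondary outcomes, and neither uses post-baseline data

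*Protocol*

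**What the plan says.** Section 15.1 covers all endpoints: "Missing data will be quantified for each endpoint broken down by treatment arm". It then sets the main assumption: "The reference analyses will assume missing at random, conditional on the baseline covariates used for adjustment". The covariates are those of the primary model, "adjusting for pre-randomisation factors of exacerbations history (number in preceding 12 months) and recruitment site", and for the secondary outcomes "Secondary endpoints will be analysed using a similar regression methodology". Multiple imputation has a conditional role: "Should the rate of missing data exceed 10%, then multiple imputation will be used in sensitivity analyses". Those sensitivity analyses are meant to allow for selection bias.

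Section 15.5 first treats participants who leave before a first exacerbation as censored in the primary analysis. It then turns to secondary and exploratory endpoints, where "a default analysis will be based on complete cases, thus assuming Missing Completely At Random". What it leaves for later is limited: "Further sensitivity analyses will be detailed in a SAP".

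The relevant data are collected repeatedly. Sections 10.5.3 and 10.5.4 schedule CAT at 3, 6 and 12 months and then about every 6 months, cough VAS at 6 months and then every 12 months, and EQ-5D-5L every 12 months. Section 10.4.3 has exacerbations reported throughout.

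**The concern.** In ordinary use, reference analysis and default analysis both mean the main analysis. The protocol attaches MAR to one and missing completely at random (MCAR) to the other, for the same endpoints, and no sentence says which prevails. Because section 15.5 defers only further sensitivity analyses, the choice of main analysis is not something the protocol leaves to the SAP. It is fixed twice, differently. Whoever writes the SAP must depart from one section, possibly once missingness by arm is known.

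The second issue is what both wordings omit. In a discontinuation trial the plausible threat is that participants who get worse stop providing questionnaires, and that this happens more often where azithromycin was withdrawn. Their worsening is partly observed beforehand in earlier CAT and cough scores and in recorded exacerbations. An analysis that conditions only on baseline variables ignores that information. If this pattern occurs, the remaining participants in the discontinuation arm look better than the whole arm, so a real harm shrinks.

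**Working it through.** **Design figures.** The protocol gives no figure for missingness in the secondary outcomes. The computable design figure is the event count, which this point does not disturb. With hazard ratio 1.25, one-sided alpha 0.027 and 90% power, Schoenfeld's formula gives 4 × (1.927 + 1.282)² / (ln 1.25)² ≈ 827 events per pair. That is 414 per arm and 3 × 414 = 1242. Allowing 5% dropout, 1242 / 0.95 ≈ 1308, against the stated 1311.

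**The two statements side by side.**

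| | Section 15.1 | Section 15.5 |
|---|---|---|
| Endpoints | each endpoint | secondary and exploratory |
| Label | reference | default |
| Assumption | MAR given baseline covariates | MCAR |
| Data used | not stated beyond those covariates | complete cases |
| Left to the SAP | – | further sensitivity analyses only |

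**Do they give different numbers?** Take an outcome at one time point and fit outcome = a + b × arm + c × covariates to the observed cases. Filling each missing value with its prediction from that fit adds points that lie exactly on the fitted surface, so b does not change. A simulation with 437 per arm confirmed this. Adjusted complete cases and MAR given the baseline covariate agreed to rounding error (differences of order 10⁻¹⁵) in every run. In SD units, with a true harm of 0.30, interim-final correlation 0.6 and base missingness of 10-20% (all assumed), both gave:

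- 0.30 under MCAR;
- 0.28 when dropout depended on the interim score in the same way in both arms;
- 0.27, 0.22 and 0.17 as dropout tied to worsening in the discontinuation arm alone strengthened (12%, 15% and 26% missing in that arm).

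MAR also using the interim score gave 0.30 throughout. So the two sections diverge numerically only if 15.5 means an unadjusted analysis or 15.1 means a repeated-measures model, and neither is stated.

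**Size on a CAT-like scale.** All inputs are assumptions, not protocol figures: SD 8, correlation 0.7 between visits, true 12-month difference 2.0 points (worse on discontinuation), and dropout after month 6 driven by the change from baseline to 6 months. Attenuation = (2.0 − estimate) / 2.0.

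| Dropout, control vs discontinuation | Baseline-adjusted complete cases | Attenuation |
|---|---|---|
| Equal | 1.96 to 2.02 | about 0% |
| 5 points more on discontinuation | 1.94 down to 1.84 | 0.06/2.0 to 0.16/2.0 = 3% to 8% |
| 15% vs 25-30% | 1.92 down to 1.61 | 0.08/2.0 to 0.39/2.0 = 4% to 20% |

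The ranges reflect how strongly dropout depends on worsening. A MAR analysis that also uses the 6-month score gave 1.96 to 2.04 throughout.

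**Dependence on the model.** The second set of runs adjusts for the baseline score, which 15.1 does not name. Without it, dropout driven by 6-month change does not bias the raw 12-month difference, but dropout driven by the 6-month level does (1.2 to 1.7 against 2.0). Change scores behave the opposite way. No complete-case form was safe under both mechanisms.

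**The case against.** The strongest reply is that this is a matter of labels. If secondary outcomes are analysed by regression on the 15.1 covariates, complete cases are already valid under the 15.1 assumption, and 15.5 merely states a stricter assumption than the method needs. That stands as far as it goes: for a single time point there may be one estimator under two names. A reader might infer that the protocol sets up two numerically opposed analyses, of which only the 15.5 one is biased. The documents do not support that, because 15.1 as worded carries the same exposure.

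A reader might also infer that the protocol itself expects dropout in this trial to be driven by exacerbations and to differ by arm. It does not say so. The remark in section 15.3 describes earlier corticosteroid withdrawal trials and is used to argue that few will leave before the first event. Sections 8.6 and 15.5 separate stopping trial medication from leaving follow-up, so dropout may be low or balanced, and with equal dropout the attenuation is about nil.

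Further limits also stand. Section 15.1 already plans imputation-based sensitivity analyses above 10% missing. Exacerbation rate is analysed per person-year, and hospital admissions and deaths are partly protected by record linkage (sections 10.5 and 10.7). EQ-5D-5L, collected every 12 months, has no earlier follow-up value at 12 months for a model to use. The trial is not powered for secondary endpoints.

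None of this ranks the two statements or brings the collected post-baseline scores into the main analysis.

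**Conclusion.** Sections 15.1 and 15.5 need reconciling, and the reconciled method should use post-baseline data. The bias is conditional. It needs dropout that follows deterioration and is more frequent in a discontinuation arm, and its size depends on the strength of both and on the model used. On the assumed CAT-like inputs above it ranges from nothing to about a fifth of the true difference, in the direction that favours discontinuation. It should not be quoted as a single expected percentage, nor as the numerical cost of the contradiction, since the unbiased comparator is a method that neither section specifies.

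The exposure is mainly CAT, cough VAS and EQ-5D-5L. The primary time-to-event analysis, its non-inferiority margin, the 1242 events and the 1311 participants are unaffected. This should be corrected, but it does not threaten the trial's main conclusion.

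**What to change.** Delete the MCAR complete-case default from section 15.5 and state the same single main method in 15.1 and 15.5. For repeated continuous outcomes, make this a likelihood-based mixed model on all observed visits, with arm-by-visit terms, the baseline score and the primary-analysis covariates. For the other secondary outcomes, name the same one assumption in both places. Keep complete-case, multiple-imputation and missing-not-at-random analyses as sensitivity analyses.

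The cost is a wording change in the protocol, matched in the SAP, and slightly more modelling on data already collected. No visits, measurements or participants are added. For EQ-5D-5L the gain at 12 months will be limited by its yearly schedule.
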